This material is the property of the University of Pennsylvania. Do not disclose or use except as authorized in writing by the study sponsor

9.3.2 Investigator reporting: notifying the Penn IRB	23
9.4 MEDICAL MONITORING	23
10 DATA MANAGEMENT	24
10.1 DATA MANAGEMENT SYSTEM DEVELOPMENT	24
10.2 DATA SECURITY.....	24
10.3 DATA PROCESSING	24
10.4 DATA QUALITY ASSURANCE.....	25
10.5 SUBJECT AND SPECIMEN TRACKING.....	25
10.6 DATA HANDLING AND RECORD KEEPING	25
10.6.1 Confidentiality	25
10.6.2 Subject Privacy/Protected Health Information	26
11 DATA AND SAFETY MONITORING.....	27
11.1 RESEARCH ROLES	27
11.2 STAFF TRAINING	27
11.3 MONITORING ACTIVITIES.....	27
11.3.1 AE/SAE Monitoring	27
11.3.2 Initial Assessment Monitoring	27
11.3.3 Protocol Monitoring	28
11.3.4 Database Auditing	28
11.3.5 Data Security	28
11.4 FREQUENCY OF DATA AND SAFETY MONITORING.....	28
11.5 AUDITING AND INSPECTING	29
12 ETHICAL CONSIDERATIONS	29
12.1 INFORMED CONSENT	29
13 RESOURCES NECESSARY FOR HUMAN RESEARCH PROTECTION	29
13.1 RESEARCH STAFF	29
13.2 STUDY FACILITIES	30
14 STUDY FINANCES	30
14.1 FUNDING SOURCE.....	30
14.2 CONFLICT OF INTEREST.....	30
14.3 SUBJECT COMPENSATION.....	30
14.3.1 Table 2. Study Compensation	30
15 REFERENCES	30

CONFIDENTIAL

This material is the property of the University of Pennsylvania. Do not disclose or use except as authorized in writing by the study sponsor

1 Study Summary

Title	The effect of sweet flavoring on the rewarding and reinforcing value of cigarillo use among young adults
Short Title	Cigarillo Flavor (FLAV)
IRB Number	843944
Methodology	This within-subjects study aims to evaluate the subjective rewarding value, the relative reinforcing value, and the absolute reinforcing value of sweet flavored cigarillos across three separate laboratory visits among 86 young adults (ages 18-24 years old) who have previously smoked \geq 10 or more cigarillos in their lifetime.
Study Center(s)	Single-center
Objectives	To determine whether the subjective rewarding value, the relative reinforcing value, and the absolute reinforcing value of sweet flavored cigarillos are greater than that of non-flavored cigarillos among young adults.
Number of Participants	Eighty-six participants
Main Inclusion and Exclusion Criteria	
Main Inclusion:
 
1. Male and female young adults who are between 18 and 24 years of age who have used \geq 10 cigarillos in their lifetime.2. Not currently undergoing smoking cessation treatment or planning to quit smoking cigarettes within the next 30 days. 
Main Exclusion:
 
3. Use of less than 10 cigarillos lifetime.4. Current enrollment or plans to enroll in a tobacco cessation program over the duration of the study.5. Current use of nicotine replacement therapy or other smoking cessation medication.6. History of substance abuse (other than nicotine dependence) in the past 12 months and/or currently receiving medical treatment for substance abuse.7. Alcohol use greater than 25 standard drinks/week.8. Use of e-cigarettes >15 days in the past 30 days.9. Women who are pregnant, breast feeding, or planning a pregnancy over the duration of the study period.10. Serious or unstable disease within the past year (e.g. cancer, heart disease).11. Lifetime history of schizophrenia or psychosis. 
The complete list of study inclusion and exclusion criteria is included within the Characteristics of the Study Population section of this protocol.

2 Introduction

This document is a protocol for a human research study. This study is to be conducted in compliance with this research protocol, as well as according to US and international standards of Good Clinical Practice (FDA Title 21 part 312 and International Conference on Harmonization

CONFIDENTIAL

This material is the property of the University of Pennsylvania. Do not disclose or use except as authorized in writing by the study sponsor

guidelines), applicable government regulations, and institutional research policies and procedures.

2.1 Background

While cigarette smoking has declined over the past two decades, cigar smoking has increased. Cigar smoking is most prevalent among young adults, with cigarillos accounting for the majority of young adult cigar use. About 13% of young adults 18-24 years old currently smoke cigarillos compared to 3.2% of adults \geq 25 years of age. Cigarillos are longer, slimmer versions of cigars that typically do not have a filter. Cigarillos expose young adults to comparable or higher levels of nicotine and many of the same toxicants and carcinogens as combustible cigarettes, making cigarillo use in young adults a significant public health concern.

The rapid growth in available flavors has popularized cigarillo use among young adults. Research suggests that young adults prefer flavored to non-flavored tobacco cigarillos, especially those flavored to taste like fruit or other sweets. However, the factors that underlie such preferences have received little attention. Qualitative studies have documented that young adults self-report positive effects associated with flavored cigarillo use, such as a pleasurable buzz, a feeling of being calm and content, and enhanced mood. Behavioral theories conceptualize the choice of sweet flavored cigarillos to non-flavored cigarillos as a reflection of greater rewarding and relative reinforcing value. Surprisingly, only two small studies have formally examined the subjective rewarding and reinforcing effects of sweet flavored tobacco, both focused on e-cigarettes. Data documenting the impact of sweet flavoring on combustible cigarillo use is critical to inform public health and regulatory actions aimed at reducing young adult cigarillo use.

Using validated human laboratory paradigms, the proposed study will break new ground by determining whether sweet flavored cigarillos are more rewarding and reinforcing (relative and absolute) than non-flavored cigarillos among young adults. We anticipate that young adults will have a greater hedonic response to sweet flavored versus non-flavored cigarillos (greater subjective rewarding value), increased motivation to consume sweet flavored versus non-flavored cigarillos (greater relative reinforcing value), and greater consumption of sweet flavored versus non-flavored cigarillos (absolute reinforcing value). These three hypotheses will be tested across three separate laboratory visits among 86 young adults (ages 18-24 years old) who have previously smoked \geq 10 cigarillos in their lifetime. We will examine whether these indices of abuse liability remain significant while controlling for other factors that may underlie the preference for flavoring. This approach will enable us to provide evidence for the impact of sweet flavored cigarillos on subjective, objective, and behavioral outcomes among young adults.

3 Study Objectives

Primary Aim: To determine whether the subjective rewarding value, the relative reinforcing value, and the absolute reinforcing value of sweet flavored cigarillos are greater than that of non-flavored cigarillos among young adults.

- H1.** Young adults will report greater subjective rewarding value from a sweet flavored versus a non-flavored cigarillo.
- H2.** Young adults will “work harder” for sweet flavored cigarillo puffs than non-flavored cigarillo puffs (i.e., higher relative reinforcing value) as measured by a relative reinforcement choice task.
- H3.** Sweet flavored cigarillos will have higher absolute reinforcing value for young adults than non-flavored cigarillos as measured by a greater number of flavored cigarillo puffs during an ad-libitum session.

Young adulthood is a critical developmental period for the onset of regular tobacco use and the establishment of lifelong use. This will be the first study to: (1) examine the rewarding and reinforcing value (both relative and absolute) of sweet cigarillo flavoring; (2) control for other

CONFIDENTIAL

This material is the property of the University of Pennsylvania. Do not disclose or use except as authorized in writing by the study sponsor

factors that may underlie the preference for flavoring; and (3) evaluate these issues in the population with the greatest cigarillo use – young adults. If the hypotheses are supported, the findings would suggest that the availability of sweet-flavored cigarillos increases cigarillo abuse liability, cigarillo use, and the overall high level of tobacco use among young adults. Novel research on cigarillo use and the role of sweet flavoring in abuse liability in this vulnerable population is critical: (1) to highlight the need for cigarillo prevention efforts and to support regulatory action on sweet flavoring; (2) to inform the content of cigarillo use interventions; and (3) to highlight potential public health harms of “grandfathered” flavored cigarillos that will remain on the market even if a ban on cigar flavoring successfully goes into effect.

4 Study Design

4.1 General Design

This within-subjects study aims to evaluate the subjective rewarding value, the relative reinforcing value, and the absolute reinforcing value of sweet flavored cigarillos across three separate laboratory visits among 86 young adults (ages 18-24 years old) who have previously smoked \geq 10 cigarillos in their lifetime. These three laboratory visits are described below.

4.2 Study Duration

Recruitment/enrollment is anticipated to begin in August 2021 and will continue for 18 months. We estimate that up to 86 participants will have completed the study by February 2023. Visits 1-3 will be completed within a 2-3 week time period. Each participant will be considered “active” until they have completed all three laboratory visits.

4.3 Laboratory Visit 1

Participants will arrive at the BBL at approximately 1:00PM. Eligible participants will document their tobacco use that day (number, time, type) and complete lifetime and past 30 day measures of cigarillo use (flavored, non-flavored, preference), tobacco use history (e.g., cigarette smoking and menthol status), as well as baseline measures of marijuana use, depression, sensation-seeking, cigarillo risk beliefs, exposure to cigarillo flavor marketing, and demographics. Participants will provide a carbon monoxide (CO) sample and a urine sample to conduct urine cotinine analysis.

Subjective rewarding value of cigarillo flavoring. Participants will be exposed to three cigarillos. Participants who are eligible and elect to participate in the study will be required to use the study-provided cigarillos during this portion of the visit in our smoking lab. One cigarillo will be non-flavored, meaning no characterizing flavors were added to the tobacco. Two will contain sweet flavoring (fruit and cream). All three will have the same characteristics, only differing by flavor. Participants will take 2 puffs from the non-flavored cigarillo, the fruit-flavored cigarillo, and the cream-flavored cigarillo. The exposure to the three cigarillos will be separated by 20 minutes each, and the order of the three exposures will be counterbalanced. Order will be stratified by sex and smoking status. After each of the three cigarillo exposures, participants will complete measures of subjective reward. Visit 1 will occur in the afternoon versus the morning to increase the likelihood that participants who smoke cigarettes smoke normally throughout the day and can rate flavoring/no flavoring in the absence of significant withdrawal symptoms. After Visit 1, participants will be scheduled for Visit 2. Participants who use tobacco (e.g., combustible cigarettes, e-cigarettes, cigars, blunts) or combustible marijuana will be given instructions to abstain from tobacco products and combustible marijuana 10 hours prior to BBL Visit 2.

CONFIDENTIAL

This material is the property of the University of Pennsylvania. Do not disclose or use except as authorized in writing by the study sponsor

4.4 Laboratory Visit 2

Relative reinforcing value of cigarillo flavoring (RRVF). Participants will arrive at the BBL at 1:00 PM and have their CO measured and provide a urine sample to conduct urine cotinine analysis. Participants who use tobacco (e.g., combustible cigarettes, e-cigarettes, cigars, blunts) or combustible marijuana will have abstained for 10 hours: CO verified < 10 ppm or < 50% of Visit 1's CO value, cotinine verified < Visit 1's cotinine value. In preparation for the assessment of the RRVF, participants will receive an introduction to a validated behavioral choice paradigm, which permits the evaluation of the preference for sweet flavored cigarillo puffs relative to non-flavored cigarillo puffs. Participants will be introduced to and briefly practice the computer task (described below) whereby they will have the chance to earn points for sweet flavored versus non-flavored cigarillo puffs. The goal is to determine the motivation to use a sweet flavored cigarillo rather than to quantify the reinforcing value of specific flavors. The sweet cigarillo flavor with the highest rewarding value (measured in Visit 1) will serve as the flavor for the assessment of the RRVF.

Participants will then begin the validated choice paradigm to assess the RRVF. Assessment of the RRVF will be accomplished by asking the participants to perform work, in the form of moving a computer mouse to hit targets on one of two computer screens to earn points toward either a sweet flavored or a non-flavored cigarillo. Using a concurrent schedule, participants will be told that they can switch from working on one screen to the other as often as they wish. Participants are instructed to move the computer mouse to have the cursor hit the targets (e.g., either a fruit labelled cigarillo or a cigarillo labeled as plain). Consistent with relative reinforcement paradigms, the reinforcement schedule in the non-flavored cigarillo earning screen will remain constant at a fixed ratio FR-25 (25 targets achieved to earn a point) while the reinforcement schedule for the sweet flavored cigarillo will increase (require more effort) with a progressive ratio schedule of PR-25x over 10 trials, such that 25, 50, 75, 100, 125, 150, 175, 200, 225, and 250 targets will have to be achieved to earn a point.

The computer task will be performed until a participant completes 10 trials and accumulates a total of 10 points from which they will earn either one puff of a non-flavored cigarillo for each point (i.e., up to 10 puffs of a non-flavored cigarillo) or one puff of a sweet flavored cigarillo for each point (i.e., up to 10 puffs of a flavored cigarillo). Participants who are eligible and elect to participate in the study will be required to use the study-provided cigarillos during this portion of the visit in our smoking lab following the RRVF task. Cigarillo puffs will be taken at the end of the procedure to prevent satiation from influencing responding in subsequent trials. RRVF is defined by the breakpoint (highest trial completed across 10 trials to earn puffs for sweet flavored versus non-flavored cigarillo puffs). To ensure that responding in the choice task is based on reinforcer preference rather than departure from the lab, the choice procedure will be followed by a 1- hour wait in the laboratory. After Visit 2 is complete, participants who use tobacco (e.g., combustible cigarettes, e-cigarettes, cigars, blunts) or combustible marijuana will be given instructions to abstain from tobacco products and combustible marijuana 10 hours prior to BBL Visit 3.

4.5 Laboratory Visit 3

Absolute reinforcing value of cigarillo flavoring. The absolute reinforcing value of a sweet flavored cigarillo as measured by an ad-libitum smoking procedure in the lab provides a measure of overall consumption. At this visit, the participant will have the opportunity to self-administer the non-flavored or the sweet flavored cigarillo that they sampled at Visit 1 and chose for the RRVF task at Visit 2. Participants who are eligible and elect to participate in the study will be required to use the study-provided cigarillos during this portion of the visit in our smoking lab. Participants will arrive at the laboratory at 1:00 PM and have their CO measured and provide a urine sample to conduct urine cotinine analysis. Participants who use tobacco (e.g., combustible cigarettes, e-cigarettes, cigars, blunts) or combustible marijuana will have abstained for 10 hours: CO verified < 10 ppm or < 50% of Visit 1's CO value, cotinine verified < Visit 1's cotinine value.

CONFIDENTIAL

This material is the property of the University of Pennsylvania. Do not disclose or use except as authorized in writing by the study sponsor

The participant will then begin a 90-minute ad-libitum cigarillo smoking paradigm for the assessment of the absolute reinforcing value of a sweet flavored cigarillo. Participants will be taken to a specially ventilated and approved smoking research room equipped with a sofa and table. Participants will be told that they will have a 90-minute laboratory waiting session where they can choose to smoke any of the color coded cigarillos placed on the table in the lab while they periodically complete questionnaires while they wait. Participants will be told that the 90-minute laboratory session will be followed by a 30-minute period of enforced abstinence from tobacco use. The labeled and color coded cigarillos will be placed on a table next to the couch. To limit brand affiliation and expectancy, the cigarillo brand identifier will be covered with tape when we color code the cigarillo for flavoring. A clock will be placed on the table showing minutes elapsed from 90 minutes. The number of cigarillo puffs (sweet flavored versus non-flavored) is the outcome variable, with consumption reflecting the absolute reinforcing value of the flavored cigarillo. Participants will be observed via an observation window by a trained research assistant who will monitor and count the number of cigarillo puffs taken (from each cigarillo) during the 90-minute period. The ad-lib session will be videotaped to independently score the number of puffs taken.

At the end of the visit, a member of the research staff will provide participants with resources on tobacco cessation services. Participants will also review educational and cigarillo cessation prevention materials that explain the study rationale and the importance of cigarillo cessation, especially as it pertains to flavored cigarillos.

5 CHARACTERISTICS OF THE STUDY POPULATION

5.1 *Target Population*

Participants will be 86 male and female young adults (ages 18-24 years old) who have used \geq 10 cigarillos in their lifetime.

We chose \geq 10 cigarillos/lifetime as a minimum criterion for participation to ensure that cigarillo exposure during the course of the study does not exceed lifetime exposure. As such, completely naïve young adults will not be exposed to cigarillos and regular cigarillo users with well-developed biases in favor of flavored cigarillos will not be included. We will measure cigarillo use history (flavor, non-flavored) and flavor preferences at baseline.

5.2 *Accrual*

We propose to recruit 100 young adults to ensure 86 participants with complete data at study end. Young adults will be recruited from the community through Internet-based advertisements (e.g., Craigslist, social media) and print advertisements including publications at 2-year and 4-year universities. Young adults who respond to the ads will be prescreened for inclusion and exclusion criteria over the telephone. In order to determine whether the ad respondents meet the inclusion criteria for lifetime cigarillo use, use of cigarillos and other tobacco products (e.g., large and little cigars) will be measured and differentiated through product description, and brand examples of the most popular brands of each product will be provided to aid accurate reporting. Research indicates that the inclusion of brand information increases self-reported cigar use. We will assess whether cigarillos and other cigar products are used as intended or modified for blunting. Cigar products modified for blunting will not count toward the inclusion cutoff for cigar exposure. The number of cigarillo blunts used in the past month and the brand characteristics (untipped, flavor) will be recorded at baseline.

Those meeting initial criteria will be screened at the beginning of Laboratory Visit 1 at the Bio-Behavioral Laboratory (BBL). After providing written informed consent, potential participants will provide a urine sample for a drug screen and a pregnancy test (females only) to determine final eligibility.

CONFIDENTIAL

This material is the property of the University of Pennsylvania. Do not disclose or use except as authorized in writing by the study sponsor

To promote participation and retention, participants will receive \$240 total for study completion (Visit 1 \$55, Visit 2 \$60, Visit 3 \$75, \$40 bonus for completing all assessments).

5.3 Inclusion Criteria

1. Able to communicate fluently in English (i.e., speaking, writing, and reading).
2. Male and female young adults who are between 18 and 24 years of age who have used ≥ 10 cigarillos in their lifetime.
3. Not currently undergoing smoking cessation treatment or planning to quit smoking cigarettes within the next 30 days.
4. Planning to live in the area (or willing to commute) for the duration of the study.
5. Willing to use study-provided cigarillos during three laboratory visits.
6. Capable of giving written informed consent, which includes compliance with the requirements and restrictions listed in the combined consent and HIPAA form.

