5.4 Exclusion Criteria

Subjects who present and/or self-report with the following criteria will not be eligible to participate in the study:

Smoking Behavior

1. Use of less than 10 cigarillos in lifetime.
2. Current enrollment or plans to enroll in a tobacco cessation program over the duration of the study.
3. Current use of nicotine replacement therapy or other smoking cessation medication.

Alcohol and Drug

1. History of substance abuse (other than nicotine dependence) in the past 12 months and/or currently receiving medical treatment for substance abuse. Counseling and support groups (e.g., Alcoholics Anonymous and Narcotics Anonymous) will not be considered medical treatment for the purposes of this protocol.
2. Current alcohol consumption that exceeds 25 standard drinks/week.
3. Breath alcohol reading (BrAC) greater than .000 at Laboratory Visit 1.
4. Use of e-cigarettes on > 15 days in the past 30 days.

Medical

1. Women, including all individuals assigned as “female” at birth, who are pregnant, breast feeding, or planning a pregnancy over the duration of the study period.
2. Serious or unstable disease within the past year (e.g., cancer, heart disease). Applicable conditions will be evaluated on a case-by-case basis by the Principal Investigator.

Psychiatric

1. Lifetime history of schizophrenia or psychosis.
2. Lifetime history of suicide attempt(s) requiring intervention AND recurring suicidal thoughts or ideations. Evaluated on a case-by-case basis by the Principal Investigator.
3. Current or recent use of anti-psychotic medications.

General Exclusion

1. Past, current, anticipated, or pending enrollment in another research program over the study period that could potentially impact subject safety, study data, and/or the study design as determined by the Principal Investigator.
2. Any medical condition, illness, disorder, adverse event (AE), or concomitant medication that could compromise participant safety or significantly impact study performance as determined by the Principal Investigator. Subjects may be deemed ineligible for any of

CONFIDENTIAL

This material is the property of the University of Pennsylvania. Do not disclose or use except as authorized in writing by the study sponsor

the aforementioned reasons at any point throughout the study, as well as during the initial telephone screen.

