Risk perceptions of flavored cigarillo use (e.g., impact of flavor on risk and addictiveness) will be measured with six Likert-style items derived from previous and ongoing research (0=not at all to 6=extremely). The Center for Epidemiologic Studies **Depression** Scale (CES-D) is a 20-item Likert- style measure with high internal consistency ($\alpha > .85$), and correlates with clinical ratings of depression severity. The CES-D has been used in adolescent and young adult tobacco studies. Young adults who use cigars such as cigarillos report higher levels of depression symptoms compared to those who do not use cigarillos. Flavoring appears to enhance the mood of young adults who use cigarillos. As such, we will not screen out for elevated depression symptoms. We will measure them and include them as a covariate in the statistical models as depression symptoms may underlie flavor preference. **Sensation seeking** will be measured with the 8-item Brief Sensation Seeking Scale (1=strongly disagree to 5=strongly agree) given its associations with little cigar and cigarillo use [47,100,150,151]. **Exposure to flavor-related advertising and marketing practices** will be measured with 9 items adapted from PATH and previous research. These items evaluate the source (e.g., Internet, social media, retail stores) and type (e.g., giveaways, direct mail and e-mail coupons, links to on-line vendors, branded merchandise, celebrity endorsement, music event sponsorship) of exposure to flavored cigarillo promotions.

Standard epidemiological items will measure lifetime and current use (monthly, weekly, daily, and rate) of **other tobacco products** such as combustible cigarettes (including menthol status), e-cigarettes, large and little cigars, and hookah. Lifetime and current use of **marijuana** (combustible, vaporized, and edible) will be assessed via items used in previous research and surveillance studies. Use of cigarillos for blunts will be measured and differentiated from cigarillo tobacco use

CONFIDENTIAL

This material is the property of the University of Pennsylvania. Do not disclose or use except as authorized in writing by the study sponsor

as intended. **Alcohol use** will be measured with epidemiological questions of lifetime, past 30 day use, as well as binge drinking episodes.

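### The 30-day quit-intention criterion names only cigarettes, so an unaided plan to quit cigarillos, the product the study administers, is not screened

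*Combined protocol and SAP*

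**What the plan says.** Section 5.3, item 3, sets the only criterion on quit intention: "Not currently undergoing smoking cessation treatment or planning to quit smoking cigarettes within the next 30 days". The Study Summary repeats it as Main Inclusion 2.

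Cigarillo exposure enters eligibility through item 2, which takes young adults "who have used ≥ 10 cigarillos in their lifetime" and sets no condition on current use. Item 5 adds "Willing to use study-provided cigarillos during three laboratory visits".

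Section 5.4 has two further cessation criteria under Smoking Behavior: "Current enrollment or plans to enroll in a tobacco cessation program over the duration of the study" and "Current use of nicotine replacement therapy or other smoking cessation medication".

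No criterion requires cigarette smoking. Smoking status is a stratification factor for exposure order (section 4.3), and cigarette smoking status is a candidate covariate (section 7.5).

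**The concern.** With a 30-day quit-intention rule, the sponsor has accepted that people about to quit should not be enrolled. The rule is attached to cigarettes, which the study does not supply, and not to cigarillos, which it does. For someone who smokes cigarillos but no cigarettes, the plan-to-quit limb can never apply.

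What is at stake is participant protection. Section 8.3.1 presents the eligibility criteria as the safeguard that keeps at-risk people out. The Visit 3 procedures (section 4.5) end with materials on the importance of cigarillo cessation, after all study exposure has taken place. The risks listed in section 8.1 do not include disruption of a planned quit attempt. A person intending to stop cigarillos is thus neither screened out nor covered by a described risk.

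**Working it through.** The plan has no figure to reproduce here; the point turns on wording. The check reads each relevant criterion against one profile: a person with at least 10 lifetime cigarillos who plans to quit cigarillos within 30 days without help and has no plan to quit cigarettes.

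| Criterion | What it tests | Does it exclude this person? |
|---|---|---|
| 5.3 item 2 | Age 18 to 24 and lifetime cigarillo count | No |
| 5.3 item 3, first limb | Current smoking cessation treatment | No, the plan is unaided |
| 5.3 item 3, second limb | Plan to quit cigarettes | No, the plan concerns cigarillos |
| 5.3 item 5 | Willingness to use the study product | Only if the person declines |
| 5.4 Smoking Behavior 2 | Enrollment, or plan to enroll, in a tobacco cessation program | No, no program is involved |
| 5.4 Smoking Behavior 3 | Current cessation medication | No, none is used |
| 5.4 General Exclusion 1 and 3 | Other research; non-compliance | No |
| 5.4 General Exclusion 2 | Investigator judgment, opening "Any medical condition, illness, disorder, adverse event (AE), or concomitant medication that could compromise participant safety" | No, a plan to quit is none of the listed grounds |

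The profile fails no criterion once willingness is stated.

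Scheduled exposure (sections 4.3, 6.2 and 8.1):

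- Visit 1: 3 cigarillos × 2 puffs = 6 puffs.
- Visit 2: 10 puffs.
- Visits 1 and 2 together: 6 + 10 = 16 puffs.
- Visit 3: ad libitum for 90 minutes; the number may be zero.

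Timing: section 4.2 places the three visits within 2 to 3 weeks, at most 3 × 7 = 21 days. The 30-day window is longer than that. A cigarillo quit date inside the same window could therefore fall during participation or shortly after it.

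**The case against.** The strongest reply is that the gap is narrow. Anyone quitting through treatment, a program or medication is already excluded, and so is anyone who plans to quit cigarettes as well. Those who remain must still agree to smoke cigarillos at three visits. The narrowing is correct. But item 5 asks about willingness and not about intention, and section 14.3 offers up to $240. A person can hold a plan to quit and still agree.

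It can also be said that the telephone script and consent text are not available for review and may ask or disclose more. That is possible, but the written criterion decides who is eligible.

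Three stronger readings are tempting, and the documents do not support them.

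- **Former users.** A reader might infer that admitting people who have already quit tobacco is the same defect. It is not. They enter because of the lifetime threshold, for which section 5.1 gives reasons. Section 7.4.2 measures rather than requires use of other tobacco products ("Standard epidemiological items will measure lifetime and current use"), and the abstinence instructions in sections 4.3 and 4.4 apply only to those who use tobacco or combustible marijuana. Admitting non-current users looks deliberate, and it is a separate choice of population.
- **Biased primary comparisons.** A reader might infer that would-be quitters distort the flavor effect. All three hypotheses compare products within the same person, and general reluctance to smoke bears on both products. At Visit 2 the non-flavored puffs stay cheap while the flavored ones become costlier, so low motivation could lower the flavored breakpoint. That is conceivable, but nothing in the documents shows it or gives it a size.
- **A head count.** A reader might want the number affected. Section 5.2 plans 100 recruits, so each percentage point is one person, but the documents give no percentage.

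**Conclusion.** The point holds in a limited form. As written, section 5.3 item 3 and its copy in the Study Summary screen a plan to quit cigarettes and leave an unaided plan to quit cigarillos unscreened. No other criterion closes that gap. A person admitted this way is scheduled for 16 puffs over two visits, followed by an optional amount at the third. Actual exposure could be lower: participants may withdraw at any time, section 7.5 assumes that 85% complete all visits, and section 8.1 lets a symptomatic participant stop mid-task.

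The conclusion rests on the criteria as printed and on the profile above. It does not depend on how common such people are. It is a cheap improvement in participant protection; the documents do not support presenting it as a threat to the primary analyses.

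**What to change.** Reconcile the plan-to-quit limb with the study product by naming cigarillos alongside cigarettes and keeping the existing 30-day window. Make the same change in section 5.3 item 3, the Study Summary and the telephone screen. Reconfirm the answer at Visit 1 before the cigarillo sampling step (item 12 in section 7.2.2). It should not be left to the Final Eligibility Checklist, which section 11.3.3 places after that visit. Final wording is for the sponsor and IRB.

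The change need not reach every tobacco product or former users; neither follows from this gap. The cost is a one-line amendment, one added screening question and probably the loss of a few otherwise eligible recruits.
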